8.2. Assessment of Adverse Events and Serious Adverse Events

The investigator or qualified sub-investigator is responsible for assessing AEs and SAEs for causality and severity, and for final review and confirmation of accuracy of event information and assessments.

8.2.1. Assessment of Causality for Study Drug and Procedures

The investigator or qualified sub-investigator is responsible for assessing the relationship to IMP therapy using clinical judgment and the following considerations:

- **No:** Evidence exists that the adverse event has an etiology other than the investigational medicinal product. For SAEs, an alternative causality must be provided (e.g., pre-existing condition, underlying disease, intercurrent illness, or concomitant medication).
- **Yes:** There is reasonable possibility that the event may have been caused by the investigational medicinal product.

It should be emphasized that ineffective treatment should not be considered as causally related in the context of AE reporting.

The relationship to study procedures (e.g., invasive procedures such as venipuncture or biopsy) should be assessed using the following considerations:

- **No:** Evidence exists that the AE has an etiology other than the study procedure.
- **Yes:** The adverse event occurred as a result of protocol procedures (e.g., venipuncture)

8.2.2. Assessment of Severity

The severity grading of AEs will be assessed as Grade 1, 2, 3, or 4 using the GSI Grading Scale for Severity of Adverse Events and Laboratory Abnormalities ([Appendix 3](#)).

For AEs associated with laboratory abnormalities, the event should be graded on the basis of the clinical severity in the context of the underlying conditions; this may or may not be in agreement with the grading of the laboratory abnormality.

8.3. Investigator Requirements and Instructions for Reporting Adverse Events and Serious Adverse Events to Gilead or CRO

Requirements for collection prior to study drug initiation:

After informed consent, but prior to initiation of study medication, the following types of events should be reported on the case report form (CRF/eCRF): all SAEs and adverse events related to protocol-mandated procedures.

Adverse Events

Following initiation of study medication, collect all AEs, regardless of cause or relationship, until 4 weeks after last administration of study drug must be reported to the CRF/eCRF database as instructed.

All AEs should be followed up until resolution or until the adverse event is stable, if possible. Gilead Sciences may request that certain AEs be followed beyond the protocol defined follow up period.

Serious Adverse Events

All SAEs, regardless of causal relationship, that occurs after the subject first consents to participate in the study (i.e., signing the informed consent) and throughout the duration of the study, including the protocol-required 24-week post treatment follow-up period, must be reported to the CRF/eCRF database and Gilead Drug Safety and Public Health (DSPH) as instructed. This also includes any SAEs resulting from protocol-mandated procedures performed after informed consent is signed.

Any SAEs and deaths that occur after the post treatment follow-up visit but within 30 days of the last dose of study IMP, regardless of causality, should also be reported. Investigators are not obligated to actively seek SAEs after the 24 week post-treatment follow-up period. However, if the investigator learns of any SAEs that occur after study participation has concluded and/or if patient is enrolled into the long term follow-up registry study (GS-US-334-1113), and/or eCRF database has been locked, and the event is deemed relevant to the use of IMP, he/she should promptly document on paper SAE form and report the event directly to Gilead DSPH within 24 hours of awareness. Gilead DSPH contact information is as follows:

Email: [contact]; or
[contact]

Electronic Serious Adverse Event (eSAE) Reporting Process

- Site personnel record all SAE data in the eCRF database and from there transmit the SAE information to Gilead DSPH within 24 hours of the investigator's knowledge of the event. Detailed instructions can be found in the eCRF completion guidelines.
- If for any reason it is not possible to record the SAE information electronically, i.e., the eCRF database is not functioning, record the SAE on the paper serious adverse event reporting form and submit within 24 hours to:

Gilead Sciences, Drug Safety and Public Health:	[contact] E-mail: [contact]
--	--

- As soon as it is possible to do so, any SAE reported via paper must be transcribed into the eCRF Database according to instructions in the eCRF completion guidelines.
- If an SAE has been reported via a paper form because the eCRF database has been locked, no further action is necessary.
- All AEs and SAEs will be recorded in the CRF/eCRF database within the timelines outlined in the CRF/eCRF completion guideline.
- For fatal or life-threatening events, copies of hospital case reports, autopsy reports, and other documents are also to be submitted by e-mail or fax when requested and applicable. Transmission of such documents should occur without personal subject identification, maintaining the traceability of a document to the subject identifiers.
- Additional information may be requested to ensure the timely completion of accurate safety reports.
- Any medications necessary for treatment of the SAE must be recorded onto the concomitant medication section of the subject's CRF/eCRF and the event description section of the SAE report form.

8.4. Gilead Reporting Requirements

Depending on relevant local legislation or regulations, including the applicable US FDA Code of Federal Regulations, the EU Clinical Trials Directive (2001/20/EC) and relevant updates, and other country-specific legislation or regulations, Gilead may be required to expedite to worldwide regulatory agencies reports of SAEs, serious adverse drug reactions (SADRs), or suspected unexpected serious adverse reactions (SUSARs). In accordance with the EU Clinical Trials Directive (2001/20/EC), Gilead or a specified designee will notify worldwide regulatory agencies and the relevant IEC in concerned Member States of applicable SUSARs as outlined in current regulations.

Assessment of expectedness for SAEs will be determined by Gilead using reference safety information specified in the investigator's brochure or relevant local label as applicable.

All investigators will receive a safety letter notifying them of relevant SUSAR reports associated with any study IMP. The investigator should notify the IRB or IEC of SUSAR reports as soon as is practical, where this is required by local regulatory agencies, and in accordance with the local institutional policy.

8.5. Special Situations Reports

8.5.1. Definitions of Special Situations

Special situation reports include all reports of medication error, abuse, misuse, overdose, reports of adverse events associated with product complaints, and pregnancy reports regardless of an associated AE.

Medication error is any unintentional error in the prescribing, dispensing, or administration of a medicinal product while in the control of the health care provider, subject, or consumer.

Abuse is defined as persistent or sporadic intentional excessive use of a medicinal product by a subject.

Misuse is defined as any intentional and inappropriate use of a medicinal product that is not in accordance with the protocol instructions or the local prescribing information.

An overdose is defined as an accidental or intentional administration of a quantity of a medicinal product given per administration or cumulatively which is above the maximum recommended dose as per protocol or in the product labelling (as it applies to the daily dose of the subject in question). In cases of a discrepancy in drug accountability, overdose will be established only when it is clear that the subject has taken the excess dose(s). Overdose cannot be established when the subject cannot account for the discrepancy except in cases in which the investigator has reason to suspect that the subject has taken the additional dose(s).

Product complaint is defined as complaints arising from potential deviations in the manufacture, packaging or distribution of the medicinal product.

8.5.2. Instructions for Reporting Special Situations

8.5.2.1. Instructions for Reporting Pregnancies

The investigator should report all pregnancies that are identified after the subject first consents to participate in the study (i.e., signs the informed consent) and throughout the study, including the post-treatment follow-up period, to Gilead DSPH using the pregnancy report form within 24 hours of becoming aware of the pregnancy.

Refer to Section 8.3 and the CRF/eCRF completion guidelines for full instructions on the mechanism of pregnancy reporting.

The pregnancy itself is not considered an AE nor is an induced elective abortion to terminate a pregnancy without medical reasons.

Any premature termination of pregnancy (e.g., a spontaneous abortion, an induced therapeutic abortion due to complications or other medical reasons) must be reported within 24 hours as an SAE. The underlying medical reason for this procedure should be recorded as the AE term.

A spontaneous abortion is always considered to be an SAE and will be reported as described in Sections 8.1 and 8.3. Furthermore, any SAE occurring as an adverse pregnancy outcome post study must be reported directly to Gilead DSPH.

The subject should receive appropriate monitoring and care until the conclusion of the pregnancy. The outcome should be reported to Gilead DSPH using the pregnancy outcome report form. If the end of the pregnancy occurs after the study has been completed, the outcome should be reported directly to Gilead DSPH. Gilead DSPH contact information is as follows:
Email: [contact] or [contact].

Pregnancies of female partners of male study subjects exposed to Gilead or other study drug must also be reported and relevant information should be submitted to Gilead DSPH using the pregnancy report form and pregnancy outcome report forms within 24 hours. Monitoring of the partner pregnancy should continue until the conclusion of the pregnancy. If the end of the pregnancy occurs after the study has been completed, the outcome should be reported directly to Gilead DSPH, [contact] or email [contact].

Clinical staff should also report any pregnancies to the Ribavirin Pregnancy Registry at 1 [contact] (see also <http://www.ribavirinpregnancyregistry.com>).

Refer to [Appendix 5](#) for Pregnancy Precautions, Definition for Female of Childbearing Potential, and Contraceptive Requirements.

8.5.2.2. Reporting Other Special Situations

All other special situation reports must be reported on the special situations report form and forwarded to Gilead DSPH within 24 hours of the investigator becoming aware of the situation. These reports must consist of situations that involve study IMP and/or Gilead concomitant medications, but do not apply to non-Gilead concomitant medications.

Special situations involving non-Gilead concomitant medications does not need to be reported on the special situations report form; however, for special situations that result in AEs due to a non-Gilead concomitant medication, the AE should be reported on the AE form.

Any inappropriate use of concomitant medications prohibited by this protocol should not be reported as “misuse,” but may be more appropriately documented as a protocol deviation.

Refer to Section 8.3 and the CRF/eCRF completion guidelines for full instructions on the mechanism of special situations reporting.

All clinical sequelae in relation to these special situation reports will be reported as AEs or SAEs at the same time using the AE eCRF and/or the SAE report form. Details of the symptoms and signs, clinical management and outcome will be reported, when available.

9. STATISTICAL CONSIDERATIONS

9.1. Analysis Objectives and Endpoints

9.1.1. Analysis Objectives

The primary objective of PK Lead-in Phase of this study is:

- To evaluate the steady state pharmacokinetics (PK) and confirm the dose of LDV/SOF FDC in chronic HCV-infected pediatric subjects

The secondary objective of PK Lead-in Phase of this study is:

- To evaluate the safety, tolerability, and antiviral activity of 10 days of dosing of LDV/SOF FDC in chronic HCV-infected pediatric subjects

The primary objective of Treatment Phase of this study is:

- To evaluate the safety and tolerability of LDV/SOF FDC +/- RBV for 12 or 24 weeks in chronic HCV-infected pediatric subjects

The secondary objectives of Treatment Phase of this study are:

- To determine the antiviral efficacy of 12 and 24 weeks of LDV/SOF FDC +/- RBV treatment in chronic HCV-infected subjects (including the impact of HCV genotype, IL28B genotype, and prior treatment experience), as assessed by the proportion of subjects with SVR 12 weeks after completion of treatment (SVR12)
- To determine the antiviral efficacy of 12 and 24 weeks of LDV/SOF FDC +/- RBV treatment in chronic HCV-infected subjects, as assessed by the proportion of subjects with SVR 4 and 24 weeks after completion of treatment (SVR4 and SVR24)
- To evaluate the kinetics of circulating HCV RNA during treatment and after completion of treatment
- To evaluate the emergence of viral resistance to LDV and SOF during treatment and after completion of treatment
- To evaluate acceptability assessed by swallowability of tablets and palatability of granules
- To evaluate the effect of growth and development on pediatric subjects during and after treatment

The exploratory objective of this study is:

- PPD

9.1.2. Primary Endpoints

For the PK Lead-in Phase, the appropriateness of the LDV/SOF FDC dose will be assessed by evaluating the steady-state PK of the LDV/SOF FDC. The primary endpoint for determining steady state PK is AUC_{τ} of GS-331007, SOF, and LDV. Additional steady-state PK parameters of GS-331007, SOF, and LDV (e.g., AUC_{last} , C_{max} , T_{max} , C_{last} , T_{last} , C_{τ} , λ_z , CL/F , V_z/F and $t_{1/2}$) will be estimated and summarized as described in Section 9.4.

For the Treatment Phase, the primary safety endpoint is any AE leading to permanent discontinuation of study drug (s).

9.1.3. Secondary Endpoints

For the PK Lead-in Phase, the secondary endpoint will include antiviral activity measurements, including assessment of HCV RNA. AEs leading to permanent discontinuation of study drug will be evaluated as a secondary safety endpoint.

For the Treatment Phase, the key efficacy endpoint is SVR12 and secondary efficacy endpoints include SVR4, SVR24, breakthrough and relapse. Additional efficacy evaluations may include HCV RNA change from Day 1; ALT normalization; and viral kinetic parameters. Secondary safety endpoints of growth and development measurements will be assessed (e.g. height, weight, and Tanner Stage Assessment). Other secondary endpoints include acceptability assessed by swallowability of tablets and palatability of granules.

9.2. Analysis Conventions

All individual subject data will be listed as measured. All statistical summaries and analyses will be performed using SAS[®] software (SAS Institute, Cary, North Carolina, USA).

9.2.1. Analysis Sets

9.2.1.1. Pharmacokinetics (PK) Analysis Sets

Intensive PK Analysis Set

The intensive PK Lead-in analysis set will include all PK Lead-in phase subjects who received at least one dose of study drug and for whom at least one non-missing PK concentration data, during the intensive sampling period, reported by PK lab. The PK analysis set will be used for detailed pharmacokinetic analysis of LDV, SOF, and metabolites.

PPD

Sparse PK Analysis Set

The PK analysis set will include all enrolled subjects who received at least one dose of study drug and for whom at least one observed concentration data of LDV, SOF, or GS-331007 are available. The PK analysis set will be used for analysis of general PK and single sample plasma concentrations.

9.2.1.2. Safety Analysis Set

The primary analysis set for safety analyses will include subjects who have received at least one dose of study drug.

Treatment-emergent data will be analyzed and defined as data collected from the first dose of study drug through the date of last dose of study drug plus 30 days.

9.2.1.3. Efficacy Analysis Set

The analysis set for antiviral activity analyses will be the Full Analysis Set (FAS) which includes HCV-infected subjects who were enrolled and have received at least one dose of study drug.

9.2.2. Data Handling Conventions

Natural logarithm transformation for key PK parameters, such as C_{max} and AUC_{tau} , will be applied for pharmacokinetic analysis.

The PK concentration values below the limit of quantitation (BLQ) will be treated as zero for the determination of summary and order statistics. Individual values that are BLQ will be presented as “BLQ” in the concentration data listing and will be excluded in any calculation of geometric means or ratios. For the presentation of summary and order statistics, if at least 1 subject has a concentration value BLQ for the time point, then the minimum value will be displayed as “BLQ”. If more than 50% of the subjects have a concentration data value BLQ for the time point, then the minimum and median values will be displayed as “BLQ”. If all subjects have concentration data values BLQ for the time point, then all order statistics (minimum, first quartile [Q1], median, third quartile [Q3], maximum) will be displayed as “BLQ”.

Missing data can have an impact upon the interpretation of the trial data. Other than the endpoints discussed below, in general, values for missing data will not be imputed.

For the analysis of post-baseline categorical efficacy endpoints, if a data point is missing and is preceded and followed in time by values that are deemed successes, then the missing data point will be termed a success; otherwise the data point will be termed a failure.

Any subject with missing data due to premature discontinuation of the study medication will be considered a failure at the time points subsequent to the date of discontinuation. If no HCV RNA values are obtained after the last dose of study medication, the subject will be considered a treatment failure for the SVR endpoints.

Where appropriate, safety data for subjects that did not complete the study will be included in summary statistics. For example,

- If a subject received study medication, the subject will be included in a summary of adverse events according to the treatment received; otherwise, if the subject is not dosed then they will be excluded from the summary.
- If safety laboratory results for a subject are missing for any reason at a time point, the subject will be excluded from the calculation of summary statistics for that time point. If the subject is missing a pre-dose value, then the subject will be excluded from the calculation of summary statistics for the pre-dose value and the change from pre-dose values.

Values for missing safety laboratory data will not be imputed; however, a missing baseline result will be replaced with a screening result, if available. If no pre-treatment laboratory value is available, the baseline value will be assumed to be normal (i.e., no grade [Grade 0]) for the summary of graded laboratory abnormalities.

Values for missing vital signs data will not be imputed; however, a missing baseline result will be replaced with a screening result, if available.

HCV RNA values below the LLOQ for the assay will be set to the lower limit minus 1 for calculation of summary statistics for the actual HCV RNA values and the change from baseline values by study visit. The reported values will be provided in the HCV RNA listing.

For selected analyses of early time point data, HCV RNA data (IU/mL) may be transformed to the logarithmic (base 10) scale (\log_{10} IU/mL).

9.2.3. Interim Analysis

Interim analyses may be performed to provide treatment regimen and duration recommendations for adolescent subjects (12 to < 18 years of age).

There will be no changes to the study design, study conduct, or the sample size as a result of the interim analysis.

9.3. Demographic Data and Baseline Characteristics

Demographic and baseline measurements will be summarized using standard descriptive methods by age group and overall for PK Lead-in phase and for Treatment Phase, respectively.

Demographic data will include sex, self-identified race/ethnicity, and age.

Baseline characteristic data will include body weight, height, body mass index, HCV RNA level (\log_{10} IU/mL), HCV genotype, prior treatment experience, and additional endpoints as necessary.

9.4. Pharmacokinetic Analysis

PK analysis will be performed for PK Lead-in phase using the intensive PK Lead-in analysis set.
PPD

The concentration data of LDV, SOF, and metabolites (GS-331007 and GS-566500) over sampling time will be listed and summarized by nominal time and cohort. Pharmacokinetic parameters (e.g., AUC_{τ} , AUC_{last} , C_{max} , T_{max} , C_{last} , T_{last} , C_{τ} , λ_z , CL/F , V_z/F and $t_{1/2}$) will be listed and summarized for LDV, SOF, and metabolites (as applicable) using descriptive statistics (e.g., sample size, arithmetic mean, geometric mean and its 95% confidence interval, coefficient of variation %, standard deviation, median, Q1, Q3, minimum, and maximum) by cohort and overall. Plasma concentrations over time will be plotted in semilogarithmic and linear formats as mean \pm standard deviation and median (Q1, Q3).

To evaluate if the steady-state PK of GS-331007, SOF, and LDV achieved in pediatric subjects of this study are similar to the exposures observed in adult subjects (Table 9-1), the GS-331007, SOF, and LDV exposure data from this study will be compared to the integrated adult data. The primary endpoint of this analysis will be evaluated by carrying out an analysis of variance (ANOVA) for log-transformed GS-331007, SOF, and LDV AUC_{τ} . The 90% confidence intervals will be constructed for the ratio of geometric means of each PK parameters. The equivalence boundary is set as 50% to 200%.

Given that dose ranging studies for SOF established that a dose of 200 mg results in suboptimal exposure compared to the 400 mg dose, and the lack of clinically significant exposure-safety relationships observed across a broad range of GS-331007 and SOF exposure, bounds of 50% to 200% for GS-331007 and SOF AUC_{τ} will allow identification of a clinically relevant difference in exposure in the pediatric population.

A phase 2 study evaluating LDV doses of 30 or 90 mg LDV in combination with DAAs VDV+TGV+RBV suggested LDV exposure may be suboptimal at the 30 mg dose based on the incidence of virologic breakthrough being approximately half in the 90 mg arm; as such the 90 mg dose was selected for further development. In the 90 mg LDV arm of this study, the LDV AUC_{τ} at the 25 percentile was 3230 hr*ng/mL. While this value is 62% lower than the mean LDV AUC_{τ} (8530 hr*ng/mL) observed in adult HCV-infected subjects in the LDV/SOF FDC Phase 2/3 population, it provides ~99.8% of maximal viral load reduction (exposure-response model established in the monotherapy proof of concept study). In the Phase 2/3 population when administered the LDV/SOF FDC, there was a lack of clinically significant exposure-efficacy or safety relationships observed across the broad range of LDV exposure. Taken together these data support the utility of bounds of 50% to 200% for LDV AUC_{τ} to identify a clinically relevant difference in LDV exposure in the pediatric population.

In all pediatric age groups, the targeted exposures for GS-331007, SOF, and LDV are the adult equivalent for which safety and efficacy has been established. In the absence of any pediatric PK

information (i.e., variability and exposure of GS-331007, SOF, or LDV is unknown) assuming a 2-fold higher variability, or a 30 % difference in GS-331007, SOF, or LDV AUC_{tau} in the pediatric population compared to adults, the predicted 90% CIs of the geometric mean ratio (GMR) will be contained within the bounds of 50% to 200%.

Individual patient management will be performed by maintaining exposures comparable to adults. In the event more than one subject in each cohort exhibits GS-331007, SOF, or LDV exposures (AUC_{tau}) less than the 2.5th percentile of adult values, a dose assessment may be required for the cohort as appropriate.

The effect of age and LDV/SOF FDC dose on PK (LDV, SOF and GS-331007) will be assessed.

Table 9-1. GS-331007, SOF, and LDV PK Parameters after Once-Daily Administration of LDV/SOF FDC in HCV-Infected Adults Subjects (Population PK Analysis from Phase 2 and 3 Studies)

Mean (%CV) PK Parameter ^a	GS-331007 (N=2113)	SOF (N=1542)	LDV (N=2113)
AUC _{tau} (ng•h/mL)	12,500 (29.2)	1380 (34.0)	8530 (60.8)
C _{max} (ng/mL)	736 (28.2)	659 (34.0)	364 (51.4)
C _{tau} (ng/mL)	N/A	N/A	247 (59.2)

a Pharmacokinetic parameters are presented as mean (%CV) and are shown to 3 significant digits.

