1.2.1.2. GS-US-337-1116

Preliminary data are available for the current study in adolescent subjects Cohort 1 (12 to < 18 years of age; N=10) and pediatric subjects Cohort 2 (6 to <12 years of age; N=12) who enrolled in the PK Lead-in Phase and received an adult clinical dose of LDV/SOF FDC 90 mg/ 400 mg or a reduced dose of LDV/SOF FDC 45 mg/200 mg, respectively. Of note, 2 out of 12 subjects (subject PPD and PPD in Cohort 2 erroneously received a dose of 90 mg/ 400 mg LDV/SOF FDC during the PK Lead-in Phase: Subject PPD received 90 mg/ 400 mg from Day 1 through Day 10 and Subject PPD received 90 mg/ 400 mg from Day 1 through Day 4 followed by the correct dose of 45 mg/ 200 mg for the remainder of the PK Lead-in Phase (Day 5 through Day 10).

Evaluation of PK in Cohort 2 subjects was conducted using data from all 12 subjects; observed LDV, SOF, and GS-331007 (primary SOF metabolite) exposures on Day 10 were used for Subject PPD and exposures were scaled to 45 mg/ 200 mg for Subject PPD (Table 1-4). Mean exposures of LDV, SOF, and GS-331007 in Cohort 1 and 2 subjects were comparable to observed exposures in the adult subjects in the Phase 2/3 LDV/SOF FDC clinical program; thereby confirming the appropriateness of the adult dose (90 mg/ 400 mg) in the adolescent population (12 to < 18 years of age) and 45 mg/ 200 mg in pediatric patients (6 to < 12 years of age) Table 1-3 and Table 1-4. The appropriateness of the 90 mg/ 400 mg LDV/SOF FDC dose in adolescents and 45 mg/ 200 mg LDV/SOF FDC dose in the pediatric patients is further supported by available safety and efficacy data in the treatment phases of the study.

Table 1-3. Steady-state PK and Statistical Comparisons of LDV, SOF and GS-331007 PK in Adolescent Subjects (PK Lead-in) and Adult Subjects (Phase 2/3 Population PK Analysis)

Mean (%CV)	Adolescents (N=10)	Phase 2/3 (N=2113)	GMR% (90% CI)
LDV			
AUC _{tau} (ng*hr/ml)	10200 (50.9)	8530 (60.8)	127 (94.9, 170)
C _{max} (ng/ml)	564 (41.2)	364 (51.4)	162 (125, 209)
C _{tau} (ng/ml)	319 (71.5)	247 (59.2)	128 (95.2, 172)
SOF*			
AUC _{tau} (ng*hr/ml)	2180 (26.6)	1380 (34.0)	160 (138, 185)
C _{max} (ng/ml)	1140 (57.2)	659 (34.0)	156 (127, 190)
GS-331007			
AUC _{tau} (ng*hr/ml)	12700 (13.7)	12500 (29.2)	105 (90.6, 122)
C _{max} (ng/ml)	1010 (21.5)	736 (28.2)	139 (120, 161)

Data reported to 3 significant figures; *N=1542

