8. PHARMACOKINETIC ANALYSES

8.1. PK Analysis in the PK Lead-in Phase (Intensive PK Analysis)

Intensive PK Analysis will be performed using the PK Lead-in Phase Intensive PK Analysis Set. Concentrations of SOF, GS-331007 and LDV from subjects in the PK lead-in Phase over sampling time will be listed and summarized using descriptive statistics (n, arithmetic mean, geometric mean and its 95% confidence interval, coefficient of variation [%CV], SD, median, Q1, Q3, minimum, and maximum) by nominal time and cohort. For Cohorts 1 and 2, plasma samples will be collected for PK analyses following dosing of study drugs on Day 10 at the following time points: 0 (predose), 0.5, 1, 2, 3, 4, 5, 8, and 12 hours postdose. For Cohort 3, plasma samples for PK analyses will be collected at the following time points: 0 (predose), 0.5, 2, 4, 8, and 12 hours postdose. PK parameters from subjects in the PK lead-in Phase will be summarized (e.g; AUC_{τ} , AUC_{last} , C_{max} , T_{max} , C_{last} , T_{last} , C_{τ} , $T_{1/2}$, volume of distribution and clearance, as appropriate) by cohort.

To confirm the appropriateness of LDV/SOF FDC dose for each age group, PK parameters for SOF, GS-331007 and LDV will be compared between each age group from this study and the LDV/SOF FDC NDA patient population (which includes population-PK derived PK exposure data from adult Phase 2 and 3 studies) by carrying out an analysis of variance (ANOVA) for log-transformed AUC_{τ} of GS-331007 and LDV as the primary endpoint and C_{max} of GS-331007 and LDV as a secondary endpoint. Geometric Mean Ratio and its 90% confidence interval will be provided.

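### The PK ANOVA makes no provision for unequal variances between 10–12 children and 2,113 adults, so the 90% intervals for the geometric mean ratio follow adult spread and their level is not assured

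*Protocol*

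**What the plan says.** Protocol 9.4 compares steady-state exposure in children with integrated adult data "by carrying out an analysis of variance (ANOVA) for log-transformed GS-331007, SOF, and LDV" AUCtau. It adds that "The 90% confidence intervals will be constructed for the ratio of geometric means of each PK parameters", and the equivalence limits are 50% to 200%. SAP 8.1 repeats the method, "by carrying out an analysis of variance (ANOVA) for log-transformed" AUCtau of GS-331007 and LDV, with Cmax "of GS-331007 and LDV as a secondary endpoint". SOF is not named in the SAP's ANOVA.

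The adult comparator is the NDA population, "which includes population-PK derived PK exposure data from adult Phase 2 and 3 studies". The children's values come from intensive sampling on Day 10.

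Neither document gives a variance structure, a Welch or Satterthwaite option, or a sensitivity analysis. The fallback in SAP 3.6 (transformed data or nonparametric methods) deals with non-normality only. Protocol 9.4 does consider different variability when planning: it predicts that the interval stays within the limits "assuming a 2-fold higher variability, or a 30 % difference in GS-331007, SOF, or LDV" AUCtau. It also has a separate trigger: if more than one subject in a cohort has AUCtau "less than the 2.5th percentile of adult values, a dose assessment may be required for the cohort as appropriate".

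**The concern.** An ordinary two-group ANOVA estimates one residual variance. Here the children contribute 9 or 11 of more than 2,100 degrees of freedom, so that estimate is the adult variance in all but name. The uncertainty in the GMR, however, comes almost wholly from the 10 or 12 children. The 90% level therefore holds only if children and adults are equally variable on the log scale.

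That is not assured. The adult values are population-PK estimates and the children's are from intensive sampling, and the protocol itself says that paediatric variability was unknown. If children are less variable, the interval is too wide. If they are more variable, it is too narrow and can fall inside 50%–200% too often. At stake are the stated level of the intervals in Protocol Tables 1-3 and 1-4, and of the Cohort 3 interval, which neither document reports.

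**Working it through.** **Inputs** (Protocol Tables 1-3, 1-4 and 9-1). Children: n=10 (Cohort 1), n=12 (Cohort 2). Adults: N=2,113 (LDV, GS-331007) and 1,542 (SOF). CVs, GMRs and 90% intervals are as printed. Exposures are assumed lognormal.

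**Formulas**
- Log SD: s = sqrt(ln(1 + CV²))
- Pooled half-width: t(0.95, n+N−2) × s_p × sqrt(1/n + 1/N)
- Welch half-width: t(0.95, Satterthwaite df) × sqrt(s₁²/n + s₂²/N)
- Log SD implied by a reported interval: [ln(upper/lower)/2] / [t(0.95, n+N−2) × sqrt(1/n + 1/N)]
- 95% interval for the child log SD: s₁ × sqrt((n−1)/χ²)

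**1. Reproduce a published interval: Cohort 1 GS-331007 AUCtau, 105 (90.6–122).** Child s = 0.136 (CV 13.7%), adult s = 0.286 (CV 29.2%), pooled s = 0.286. Half-width = 1.646 × 0.286 × 0.317 = 0.149, giving 90.5–121.9. That matches within rounding.

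**2. Same row with separate variances.** Standard error = sqrt(0.136²/10 + 0.286²/2113) = 0.0436; df = 9.4; t = 1.825; half-width = 0.0795, giving 97.0–113.7. The reported interval is 0.149/0.0795 = 1.87 times as wide on the log scale.

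**3. All six AUCtau rows**

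| Row | Child / adult log SD | Implied log SD | Reported | Pooled | Welch |
|---|---|---|---|---|---|
| C1 LDV | 0.480 / 0.561 | 0.559 | 94.9–170 | 94.8–170.1 | 96.1–167.8 |
| C1 SOF | 0.261 / 0.331 | 0.281 | 138–185 | 134.6–190.1 | 137.4–186.3 |
| C1 GS-331007 | 0.136 / 0.286 | 0.285 | 90.6–122 | 90.5–121.9 | 97.0–113.7 |
| C2 LDV | 0.538 / 0.561 | 0.566 | 66.5–114 | 66.5–113.5 | 65.7–114.9 |
| C2 SOF | 0.291 / 0.331 | 0.289 | 101–133 | 99.1–135.8 | 99.7–134.9 |
| C2 GS-331007 | 0.309 / 0.286 | 0.286 | 56.9–74.7 | 56.9–74.7 | 55.5–76.5 |

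LDV and GS-331007 reproduce from one pooled variance. For GS-331007 the implied SD is 0.285 and 0.286 in the two cohorts, although the children's own SDs are 0.136 and 0.309. SOF AUCtau does not reproduce from the printed adult CV, so nothing is claimed from those rows. In Cohort 2, two children received 90/400 mg in error, and for one of them "exposures were scaled to 45 mg/ 200 mg"; the table footnote reports similar results without them.

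**4. Is there evidence of unequal variance?** For Cohort 1 GS-331007 the 95% interval for the child log SD is 0.094–0.249, which excludes the adult 0.286. In the other five AUCtau rows the interval includes the adult value.

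**5. What the pooled interval does if children are more variable** (simulation, n=10, LDV, 1,000,000 runs per scenario)

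| Child CV / adult CV | Pooled coverage | Welch coverage | Pooled pass rate at true GMR 50% (nominal 5%) |
|---|---|---|---|
| 1 | 90% | 90% | 5.0% |
| 1.25 | 83% | 90% | 8.5% |
| 1.5 | 77% | 90% | 11.7% |
| 2 | 67% | 90% | 16.5% |

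At the same three raised ratios the pooled pass rates are 9.0%, 12.8% and 18.7% for SOF and 9.1%, 13.0% and 19.1% for GS-331007. Also requiring at most one child below the adult 2.5th percentile lowers them to 6.1%, 6.8% and 6.8% (LDV) and to below 1% (SOF and GS-331007). That trigger does not act on high exposure: at a true GMR of 200% and twice the CV, the pooled pass rate is 14–19% with the rule, against 4–5% with Welch.

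**6. A non-primary row in the other direction.** Cohort 1 SOF Cmax (child CV 57.2%, adult 34.0%) is reported as 127–190; Welch gives 114.6–212.4. The child log SD interval, 0.366–0.971, excludes the adult 0.331 but not the 0.386 implied by the reported interval. SOF Cmax is outside the SAP's ANOVA. Cohort 1 LDV Cmax was already reported at 125–209, so Cmax was not used as a gate.

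**The case against.** Four points can be made in the plan's favour.

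- **The data hardly contradict equal variances.** Chi-square tests of the six child AUCtau log SDs against the adult values give p = 0.64, 0.45, 0.019, 0.96, 0.66 and 0.61. The one small value is 0.11 after Bonferroni correction for six rows, and in that row the reported interval errs on the wide side. This stands. It also means the ratio of 0.85 for Cohort 2 GS-331007 is conditional on taking the child SD of 0.309 at face value: about half of the shortfall is only the change of critical value (1.646 to 1.794).
- **The cohort geometric mean with its 95% interval is already planned**, and it uses only the children's spread. True, but it is not the 90% GMR interval that is set against 50%–200%.
- **Twofold variability was considered.** It was, but only as a planning check; the analysis model stays the same. The check itself holds: for LDV at twice the CV and n=10, the predicted Welch interval around a GMR of 100% is 57.5%–173.8%.
- **Too-frequent passing is hypothetical.** It needs children more variable than adults, whereas the observed AUCtau CV ratios are 0.47–1.08. The low-exposure trigger removes most of the excess, and the protocol reports no clinically significant exposure–safety relationship. This stands, and it is why the point is minor.

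**Conclusion.** The concern holds, as a minor one. The plan specifies an ANOVA with no allowance for unequal variances, and the published LDV and GS-331007 AUCtau intervals behave as adult-variance intervals. Their 90% level is right only if children and adults are equally variable. Compared with separate variances, the visible error runs from 1.87 times as wide (Cohort 1 GS-331007) to 0.85 times as wide (Cohort 2 GS-331007).

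No Cohort 1 or 2 AUCtau conclusion against 50%–200% changes. SAP 1.2.1 and 1.2.2 describe Cohort 3 dosing and dose confirmation as past, so what is affected is the reported intervals and the strength of the similarity statement, not a pending dose decision.

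The conclusion rests on lognormal exposures, on log SDs derived from printed CVs, and on inferring a pooled variance from the word ANOVA and the reproduced intervals, since the variance model is not printed.

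**What to change.** Add to SAP 8.1, and to Protocol 9.4 if it is amended: GMRs and 90% confidence intervals will be computed on the log scale with separate residual variances for paediatric and adult subjects (Welch, or PROC MIXED with REPEATED / GROUP= and Satterthwaite degrees of freedom), for each of the three cohorts; the pooled-variance 90% interval will be shown beside it for continuity with Protocol Tables 1-3 and 1-4.

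The planning sentence in Protocol 9.4 can stay as a predicted interval. It should not be read as a likely outcome: for LDV at twice the adult CV, n=10 and a true GMR of 1, the chance that the Welch interval lies inside 50%–200% is about 39%.

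The cost is one model option and one sentence, with no new data. There is some loss of containment. For LDV at a true GMR of 1 and n=10, it goes from about 97.5% to 94.7% if variances are equal, from 93.9% to 82% at 1.25 times the adult CV, from 89.6% to 66% at 1.5 times, and from 81.5% to about 39% at twice. At twice the CV, SOF goes from 99.2% to 89.6% and GS-331007 from 99.8% to 96.2%. That loss is the real imprecision of 10 children, which the pooled interval hides.
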